3.2 EXCLUSION CRITERIA

A potential participant who meets any of the following criteria will be excluded from participation in the study:

- Radicular Pain
- Diagnosis of eating disorder (current or within the past 6 months)
- Diagnosis of OCD (lifetime)
- ADHD (currently under treatment)
- Neurological disorders and conditions, including, but not limited to:
 - History of epilepsy
 - Seizures (except childhood febrile seizures and ECT-induced seizures)
 - Dementia
 - History of stroke
 - Parkinson's disease
 - Multiple sclerosis
 - Cerebral aneurysm
 - Brain tumors
- Medical or neurological illness or treatment for a medical disorder that could interfere with study participation (e.g., unstable cardiac disease, HIV/AIDS, malignancy, liver or renal impairment)
- Prior brain surgery

- Any brain devices/implants, including cochlear implants and aneurysm clips
- Traumatic brain injury
- (For females) Pregnancy or breast feeding
- Anything that, in the opinion of the investigator, would place the participant at increased risk or preclude the participant's full compliance with or completion of the study

Justifications for any exclusions based on race, gender, or ethnicity: Non-English speaking individuals are excluded because the ability to accurately and completely communicate study information, answer questions about the study, and obtain consent are necessary.

Justification for excluding women or women who become pregnant: Pregnant participants will be excluded despite the fact that theoretical risk to mother or fetus is exceedingly small, since no safety data for pregnancy is known to exist for tDCS/tACS studies. We will verify pregnancy status via a urine pregnancy test for all female participants prior to receiving treatment on Day 1 of Stimulation.

3.3 STRATEGIES FOR RECRUITMENT AND RETENTION

3.3.1 RECRUITMENT

This clinical trial will utilize multiple recruitment strategies in order to communicate this opportunity to as many potential participants as possible. Participants will be recruited from the following sources using IRB approved flyers and email scripts:

- UNC University Physical Therapy clinic locations
- UNC Hospital and Carolina Data Warehouse
- North Carolina Institutions of Higher Learning

The UNC community will also be notified of the study through the informational notify.unc.edu system and a research listing will be created on <http://allyresearch.org/> as well as on <http://jointheconquest.org>. A short description of the study will also be included on the [name] lab website. We will also have a posting on the [name] lab website.

The prevalence of chronic LBP in North Carolina has increased from 1992 to 2006 as it more than doubled in the 14 year interval from 3.9 to 10.2 percent (Freburger et al., 2009). Studies have also documented increases in visits to physicians, physical therapists, and chiropractors (Martin et al., 2008). UNC Healthcare has a chronic pain clinic as well multiple physical therapy locations allowing local access to a large chronic pain population.

3.3.2 RETENTION

[figure not shown]
Our retention strategy includes a payment schedule of two times per participant. The participant will receive payment on both days of stimulation. The research staff will also give each participant a reminder call or email for the day 1 of stimulation and day 2 of stimulation. Each research staff member will be easily available for the participants to contact via email or phone.

The inclusion criteria state that each participant must be able to understand all risks and benefits associated with this study. We will be asking each participant to answer questions about the consent form to determine that the study process and the duration of participation are completely understood by all participants. We will aim to have a specific research team member assigned to complete all sessions with the same participant to establish rapport and encourage the participant to continue attending sessions. The study team will work hard at forming a professional relationship with each participant so that they feel comfortable and willing to discuss what may be sensitive information. Retention will be quantified by the fraction of participants coming to each scheduled session (the data from each session will be scored and documented the day of the session).

4 BASIC STUDY DESIGN

This study is a pilot clinical trial with a randomized, double-blind, crossover design. This is a single site study with 2 arms. We estimate six months to complete study enrollment.

Figure 1.

Active sham treatment will include 10 seconds of ramp-in to 1 minute of 10 Hz tACS with a ramp-out of 10 seconds for a total of 80 seconds of stimulation. The choice of an active sham is motivated to enhance success of patient blinding by mimicking skin sensations associated with tACS. 10 Hz tACS will have a 10 second ramp-in and ramp-out with 40 minutes of stimulation for a total of 2420 seconds of stimulation. Stimulation waveform is a sine-wave with peak-to-peak amplitude of 2 mA. In both arms, participants will stay in a relaxed yet controlled state by watching a nature movie (“Reefscape”) during stimulation.

Eligible participants who complete this clinical trial will have a total of 2 visits; 2 days of stimulation (with 1-3 weeks in between). Day one of stimulation will take approximately 2.5 hours as eligibility will be confirmed at the beginning. Day 2 of stimulation will take approximately 2 hours. Two days after each stimulation day, participants will receive via email a follow-up survey to complete that will take approximately 15 minutes. We estimate that total participation will be approximately 6 hours over the course of 6 weeks. All time estimates take into consideration breaks and time variance in administration.

4.1 TREATMENT ASSIGNMENT PROCEDURES

Participants will be randomized into one of 2 arms (*see Figure 1 above*). This is a double-blind study, so neither the participant nor the research will know which treatment the participant is receiving, if any.

4.1.1 RANDOMIZATION PROCEDURES

[name] will randomize 6-digit stimulation codes which will be used by the study coordinator and research assistants and will be linked to the participant numbers of enrolled participants. These stimulation codes are directly linked to which treatment participants receive (sham or 10 Hz tACS) and will be used with the XCSITE100 stimulator. An unblinded code sheet that matches these stimulation codes to treatment arm will be kept by [name] and will not be available to the study coordinator or research assistants.

The unblinded code sheet will have the following information:

1. The initial identifier codes for all potential participants
2. Stimulation code: 6-digit numerical code for the stimulation session
3. Condition number: Numerical code for the condition
4. Condition name: Name of the condition

A copy of this code sheet with condition number and condition name REMOVED is provided to the study coordinator and research assistants. This blinded code sheet will be used to ensure the correct stimulation code is provided for each session.

These linked codes ensure that the study coordinator and research assistants are kept blinded to which treatment each participant receives. Please see *Data and Safety Monitoring* for more information on unblinding this information.

5 STUDY SCHEDULE

In order to increase data quality, the assessments for an individual participant will be administered by the same researcher.

It is important to note that consent, scales, and experiments will all take place in a private room. Any phone calls will take place in a private lab environment as well.

5.1 SCREENING

The screening process has been divided into two steps: phone screening and an initial session. The phone screening allows researchers to screen out participants based on self-report responses and for potential participants to become familiar with the study schedule, including procedures. The initial session allows researchers to confirm any preliminary diagnoses and assess for exclusion criteria that cannot be confirmed via phone.

5.1.1 SCREENING TELEPHONE CALL

During the telephone screening, researchers will provide a brief background about chronic pain and tACS. The timeline of visits will be explained, including the number of visits and the time commitment required. The participant will be informed of compensation, both amount and payment schedule. The participant will be asked if they have any questions. Once all questions have been answered, the participant will be asked if he/she is still interested in participating in the study. If yes, the researcher will ask if the participant will provide verbal consent to begin the initial phone screening which will determine eligibility for the initial session. *A telephone script, which includes the screening questions, is provided in Appendix G.* If the participant meets initial criteria with these two assessments, the initial session will be scheduled and a reminder call or email will be given at least 24 hours before the initial session.

5.1.2 INITIAL SCREENING SESSION (VISIT 1)

At day 1 of stimulation, participants will be guided through the consent form and the HIPAA authorization form and be given the time to ask any questions about the information discussed. To ensure that all aspects of the research are understood, participants may be asked a series of questions about the research they are about to take part in (*Appendix E*). Once it is clear that the participant understands the consent form and HIPAA authorization, they may sign the forms.

Following the consent process, the participant completes the ODI and DVPRS to measure disability and pain intensity on 0-11 scale. The HAM-D and DASS-21 will assess low suicide risk and depression level. The self-report measures: UCLA Activity Score, PCS, and PSEQ will assess physical activity limitations, pain experience, and confidence in daily activities. Data on demographics, handedness, stai, bis-bas, and opinion pre-treatment will also be collected.

Once eligibility has been confirmed and all relevant data collected, Day 1 of stimulation will begin.

5.2 STIMULATION SESSIONS

5.2.1 DAY 1 OF STIMULATION (VISIT 1 CONTINUED)

Prior to starting any study procedures, female participants will be asked to take a urine pregnancy test to ensure continued eligibility. The 5xSST, FTF, and pressure pain threshold test will be administered before stimulation. A resting state EEG will be recorded for 5 min before and after stimulation. The participant will receive 40 minutes of sham or 10 Hz tACS stimulation (as per the initial randomization) while watching “Reefscape”. The stimulation will be followed by the pressure pain threshold, 5xSST, FTF, stimulation adverse effects questionnaire and perceived improvement ending the session.

5.2.2 DAYS 2 OF STIMULATION (VISIT 2)

Prior to starting any study procedures, female participants will be asked to take a urine pregnancy test to ensure continued eligibility. The ODI, DVPRS, 5xSST, FTF, and pressure pain threshold test will be administered before stimulation. A resting state EEG will be recorded for 5 min before and after stimulation. The participant will receive 40 minutes of sham or 10 Hz tACS stimulation (as per the initial randomization) while watching “Reefscape”. The stimulation will be followed by the pressure pain threshold, 5xSST, FTF, stimulation adverse effects questionnaire and perceived improvement ending the session.

5.3 FOLLOW-UP

5.3.1 FOLLOW-UP EMAIL

Two days after both sessions of stimulation, participants will receive an email with a follow up survey to assess any change in pain perception. The ODI and DVPRS will take approximately 15 minutes to complete.

5.3.2 UNBLINDING PROCEDURES

There are no current plans to systematically unblind participants to the treatment they may or may not have received during the clinical trial. However, following the completion of data collection, participants may contact the [name] Lab for unblinding information.

6 STUDY PROCEDURES/EVALUATIONS

6.1 SELF-REPORT MEASURES

During the initial session, researchers will collect demographics, which include medical history and medication history. In addition, several other self-report measures will be used throughout this study. These measures are listed below and can be found in the attached documents.

- A. OSWESTRY DISABILITY INDEX (ODI) is a 10 item self-report assessment to measure level of disability and monitor change over time. It takes only 5 minutes to complete with a MCID of 10 pts. (Fritz et al., 2001)
- B. DEFENSE AND VETERANS PAIN RATING SCALE (DVPRS) is a modified numeric rating scale with faces and word descriptors. The MCID is 2 pts. It also includes supplementary questions on the impact of chronic pain on other aspects of daily living (Buckenmaier et al., 2013).
- C. UCLA ACTIVITY SCORE is a self-report measure of 1 question to measure activity level and change.
- D. PAIN CATASTROPHIZING SCALE (PCS) is a 13 item self-report measure designed to quantify an individual's pain experience.(Sullivan et al., 1995)
- E. PAIN SELF-EFFICACY QUESTIONNAIRE (PSEQ) is a 10-item questionnaire measuring confidence in ability to perform specific tasks or coping with pain (Nicholas, 2007)
- F. DEPRESSION ANXIETY STRESS SCALE (DASS-21) is a 21 item short form self-report questionnaire (Original DASS is 42 items) that provides a quantitative measure of depression, anxiety, and stress experienced in the past week. It is important to note that the DASS-21 is not a diagnostic tool (Lovibond & Lovibond, 1995).

6.2 CLINICAL MEASURES

In addition to self-report measures, several clinical measures will be used throughout this study, both for measuring change over time and for diagnostic use. These measures are listed below and can be found in the attached documents.

- A. HAMILTON PSYCHIATRIC RATING SCALE FOR DEPRESSION (HAM-D) is a 21-item assessment to rate the severity of depression in patients (Hamilton, 1960). This measure is being used to assess levels of depressive symptoms and to determine suicide risk. Low suicide risk for this study is defined as scoring 2 or less on the Suicide question on this assessment.
- B. FIVE TIMES SIT-TO-STAND TEST (5xSST) is a quick and easy to administer test of an individual's ability to transition between sitting and standing five times in a row and has been previously tested in chronic LBP populations. We will use as a measure of functional lower limb muscle strength and in quantifying functional change of transitional movements with MCIS between 4-9 seconds (Simmonds et al., 1998, Andersson et al., 2010) .
- C. FINGERTIP-TO-FLOOR TEST (FTF) is a valid, reliable, and responsive test in individuals with chronic low back pain. It measures trunk flexion and the MCIC varies (approx. 10 cm) (Perret et al., 2001)

6.3 SPECIAL ASSAYS OR PROCEDURES

6.3.1 SPECIAL PROCEDURES

Each participant will attend two days of stimulation for this study. Each participant will be randomly assigned to one of two treatment arms (sham or 10 Hz tACS) then the opposite on the second visit. For more information on the stimulation procedures, see section 7.2 *Preparation and Administration of Study Investigational Product*.

6.3.2 EKG PROCEDURES

To obtain a measure of the heart rate during both stimulation conditions, ECG electrodes as part of the EEG acquisition system are placed on the participant's body. Ideally one electrode will be placed below the left collarbone and a second below the right chest. The EKG will be recorded for the full 40 minutes stimulation session during spontaneous breathing and will be divided into 10 minute intervals for analysis. A standard spectral analysis will be applied to a 10-minute interval, including total power, HF, LF, and VLF. The HF component reflects the parasympathetic modulation of the heart rate.

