12.4 DATA MANAGEMENT RESPONSIBILITIES

The responsibilities designated to each member of the research team are documented on the Delegation of Authority Form. The study coordinator and research assistants will be responsible for the informed consent process, review for eligibility, questionnaire administration, data entry, device administration, and EKG administration. The study coordinator will be responsible for AE/SAE documentation and reporting, while the PI will be responsible for the AE assessment, review of the AE documentation forms, and overview of the research staff. [name] will be the medical monitor for the study.

REDCap will serve as a secure data management tool for this study. The study coordinator and research assistants will have complete access to the REDCap system, while the PI and Co-I will have read-only ability. This will enable to researchers to enter the data and the PI and Co-I to review.

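### EKG recorded during stimulation carries 10 Hz current for far longer in active than in sham: settle the HRV window, plan for artefact, and mask the live trace

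*Combined protocol and SAP*

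**What the plan says.** **Recording.** Section 6.3.2 states that "ECG electrodes as part of the EEG acquisition system are placed on the participant's body", and then: "The EKG will be recorded for the full 40 minutes stimulation session during spontaneous breathing and will be divided into 10 minute intervals for analysis". Section 7.2 also has heart rate recorded throughout stimulation, there as a covariate.

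**Current.** Section 4 gives the active condition as follows: "10 Hz tACS will have a 10 second ramp-in and ramp-out with 40 minutes of stimulation for a total of 2420 seconds of stimulation". The sham ramps in over 10 seconds and then delivers "1 minute of 10 Hz tACS with a ramp-out of 10 seconds for a total of 80 seconds of stimulation". The waveform is a 2 mA peak-to-peak sine.

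**Analysis window.** Section 11.1 applies the HRV spectral analysis to intervals before and after stimulation. The primary hypothesis in 2.4.1 compares HF between active and sham.

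**Staff and blinding.** Section 12.4 gives the coordinator and research assistants "questionnaire administration, data entry, device administration, and EKG administration", among other duties. Section 5 adds that "the assessments for an individual participant will be administered by the same researcher". Sections 5.2.1 and 5.2.2 put pressure pain threshold, 5xSST and FTF after stimulation. Section 4.1.1 keeps these staff blinded through coded stimulation files. Section 7 assigns waveform validation to separate unblinded individuals who have no contact with participants. The document does not mention EKG artefact handling, R-peak checking or who can see the EKG trace.

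**The concern.** Two separate routes lead from the same recording arrangement.

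**Measurement.** 10 Hz is far above the HF band of the beat-interval series (0.15-0.40 Hz), so stimulation does not enter HF power directly. It can enter through beat timing. A 10 Hz sine added to the EKG moves the apparent R-peak, and random timing error adds power that is weighted towards higher frequencies. The hypothesised effect is a rise in HF under active stimulation, so the error would act in the direction the trial hopes to see, and mostly in one condition. Section 11.2 intends the results to size later trials, so an artefactual difference would carry forward.

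**Blinding.** Section 7 treats sight of the stimulation waveform as something to keep away from anyone who meets participants. A visible EKG trace with 10 Hz pickup could give the assessing researcher the same information: a sine that persists in one session and stops after 80 s in the other. In a two-period crossover, recognising one session identifies both.

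**Working it through.** **1. Durations (section 4).** Active: 10 + 40 × 60 + 10 = 2420 s. Sham: 10 + 60 + 10 = 80 s. Both agree with the document. Ratio: 2420/80 = 30.25.

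**2. Overlap with the 6.3.2 intervals** (600 s each, assuming recording starts with the current).

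| Interval | Active | Sham |
|---|---|---|
| 1 | 600/600 s | 80/600 s = 13.3% |
| 2, 3, 4 | 600/600 s each | 0 |

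With windows before and after stimulation (11.1), overlap is 0 s in both conditions.

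**3. Is there EKG for the 11.1 windows?** Sections 6.3.2 and 7.2 describe EKG only during stimulation. The only recording described before and after is a 5-minute resting EEG (5.2.1, 5.2.2), which is shorter than the 10-minute interval in 6.3.2. So 11.1 names windows for which no EKG acquisition is specified.

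**4. R-peak jitter (assumed inputs).** The document gives no pickup amplitude, filter or beat-correction rule. Assume a Gaussian R-wave (SD 10-12 ms) plus a 10 Hz sine of random phase, with the peak taken as the maximum within 40 ms:

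- pickup 25% of R-wave height: jitter SD 1.1-1.6 ms
- pickup 50%: 2.3-3.4 ms
- pickup 100%: about 24 ms, where beat detection breaks down.

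**5. Jitter to HF power.** For independent timing error of SD σ and mean beat interval T,

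added HF = 8σ²T ∫ sin²(πfT) df, over 0.15-0.40 Hz.

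With T = 0.85 s the integral is 0.1132.

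- σ = 1.1 ms: 8 × 1.21 × 0.85 × 0.1132 = 0.93 ms², which is 0.3% of a true HF of 300 ms² and 1.9% of 50 ms².
- σ = 3.4 ms: 8 × 11.56 × 0.85 × 0.1132 = 8.90 ms², which is 3.0% of 300 ms² and 17.8% of 50 ms².

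Simulated 10-minute records without filtering agree. At 50% pickup, HF in an active interval is multiplied by 1.03 (true HF 300), 1.11 (100) and 1.22 (50), and in the first sham interval by 1.00-1.02. At 100% pickup the active multiplier is 2.4-9.3 and the first-interval sham multiplier 1.13-1.81.

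**6. Effect on a test.** The plan states no alpha or SD. Assume a paired t-test on log HF, n = 20, two-sided 0.05, SD of the paired difference 0.4-0.8, and the same bias in every participant. The noncentrality is ln(1 + bias)/SD × √20.

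| Spurious rise | Noncentrality (SD 0.8 to 0.4) | False-positive rate |
|---|---|---|
| 3% | 0.17 to 0.33 | 5.3-6.1% |
| 10% | 0.53 to 1.07 | 8-17% |
| 18% | 0.93 to 1.85 | 14-42% |

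**The case against.** The strongest reply is that 11.1, the statistical plan itself, puts the primary HRV analysis before and after stimulation, where no current flows. On that reading the measurement route closes and needs no filter. This stands: the bias is conditional on using the 6.3.2 intervals. It does not settle the matter, because the only EKG acquisition described is during stimulation.

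The size of the bias is also assumed. Stimulation electrodes sit at F3, F4 and CZ (7.2) and the EKG electrodes on the chest (6.3.2), so pickup may be well below 25% of R-wave height. At the mild end of the range the test keeps essentially its nominal error rate. The 18% figure is one corner: low true HF and the largest jitter. Pickup large enough to multiply HF several-fold would more probably show up as unusable records than as a hidden bias.

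On blinding, nothing says that a live trace is displayed or watched, and 7 already separates waveform validation from participant contact. The assessor-run tests are neither primary nor secondary outcomes. The primary is computed by software. The secondary is self-reported pain from the DVPRS, which 5.2.1 and 5.2.2 do not list after stimulation and 5.3.1 collects by email. All of this stands and limits the consequence.

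A reader might infer that the artefact is present in active only. The documents do not support that, since sham also carries 10 Hz current for 80 s; the contrast is active-only in intervals 2 to 4.

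**Conclusion.** The point holds as a conditional weakness that is cheap to remove. Sections 6.3.2 and 11.1 name different HRV windows and must be reconciled. If the during-stimulation intervals supply HF, exposure to 10 Hz current differs by a factor of 30.25, and HF can be distorted far more in active than in sham. Under assumed pickup of 25-50% of R-wave height, without filtering, the inflation is about 0.3% to about 20%. Pickup size is the unknown that decides where in that range, or outside it, the trial falls.

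A reader might go further and conclude that the primary result can be positive from instrument error alone, or that the researcher will be unblinded. The documents support neither. The first needs the 6.3.2 windows to override 11.1 and pickup to be substantial; the second needs a trace that staff can see. What the documents do show is that no safeguard covers the EKG trace under either window, while the same researcher goes on to run pressure pain threshold, 5xSST and FTF. The named outcomes would be affected only indirectly by that route.

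**What to change.** 1. In 6.3.2 and 11.1, state one HRV window. EKG recorded before and after stimulation, with no current flowing, is preferable because it removes the overlap in both conditions. Specify that recording and its length.
2. After a signal check before stimulation, hide the live EEG/EKG display from the assessing researcher for the 40 minutes. The side-effect monitoring in 8.2.2, 8.3 and 10.1 relies on asking the participant, not on the trace, so it is unchanged.
3. If during-stimulation intervals are used, drop the first interval in both conditions, process every record identically, do R-peak checking and beat correction blind to condition, and report the percentage of corrected beats by condition. Check any 10 Hz filter first for its own effect on R-peak timing, because 10 Hz lies within the frequency range of the QRS complex.

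**Cost:** protocol wording, a display setting and a processing rule, plus short recordings before and after stimulation if that window is chosen. A loose lead may go unnoticed until the session ends, and under item 3 one of four intervals is lost.

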2.4 STUDY AIMS/HYPOTHESES

2.4.1 PRIMARY OBJECTIVE

NULL HYPOTHESIS. There is no difference in parasympathetic tone in Heart Rate Variability, shown by an increase in high frequency input via spectral analysis on EKG recordings between active and sham stimulation.

ALTERNATIVE HYPOTHESIS. There is a difference in parasympathetic tone in Heart Rate Variability, shown by an increase in high frequency input via spectral analysis on EKG recordings between active and sham stimulation.

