11 STATISTICAL PLAN

11.1 STATISTICAL ANALYSIS STRATEGIES

Our study design is a AB/BA crossover and we will ensure a washout effect by scheduling 1-3 weeks between stimulation sessions. A continuous outcome approach will be used to analyze the crossover trial data where carryover effects will be assumed to be equal.

Primary outcome: Use kubios software to analyze HRV over before and after stimulation. A standard spectral analysis will be applied to the pre and post intervals, including total power, HF, LF, and HP. Specifically looking at the HF component since it reflects the parasympathetic modulation of the heart rate. Use a repeated measure ANOVA with factor session (1 vs 2) and factor treatment (active vs sham) (R software). We hypothesize a treatment main effect and with no session effect and no interaction.

Secondary outcome: A Mann-Whitney-Wilcoxon rank-sum testMann Whitney U test (R software) will be performed on the self-report VAS pain scale (nonparametric scale) (from DVPRS) before and after stimulation as well as between sessions to analyze any differences in self-report perceived pain. Grouped ANOVAs and unpaired t-tests may also be used to analyze correlations within other self-report measures

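### The primary HF outcome is defined on pre and post intervals (11.1), but the protocol describes EKG recording only during the 40-minute stimulation (6.3.2, 7.2)

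*Combined protocol and SAP*

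**What the plan says.** **Recording.** Section 6.3.2 gives the purpose of the EKG as "To obtain a measure of the heart rate during both stimulation conditions". It uses "ECG electrodes as part of the EEG acquisition system", and the signal is "recorded for the full 40 minutes stimulation session during spontaneous breathing and will be divided into 10 minute intervals for analysis". The analysis sentence there reads "A standard spectral analysis will be applied to a 10-minute interval, including total power, HF, LF, and VLF". Section 7.2 has heart rate recorded for the duration of stimulation and describes it as a covariate.

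**Analysis.** Under the primary outcome, section 11.1 says "Use kubios software to analyze HRV over before and after stimulation" and then "A standard spectral analysis will be applied to the pre and post intervals, including total power, HF, LF, and HP". The test is "Use a repeated measure ANOVA with factor session (1 vs 2) and factor treatment (active vs sham", run in R.

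**Hypothesis.** Section 2.4.1 speaks of a difference in parasympathetic tone "shown by an increase in high frequency input via spectral analysis on EKG recordings between active and sham stimulation". It names no time window.

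**Visit procedures.** Sections 5.2.1 and 5.2.2 schedule a 5-minute resting EEG before and after stimulation and do not mention EKG. The EEG Procedures text after 6.3.3 gives the purpose of those blocks as detecting neurophysiological change. Section 12.4 lists EKG administration among staff duties without saying when. Appendix A has no EKG row.

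**The concern.** The section that tells staff what to record and the section that tells the analyst what to analyse describe different measurements of the primary outcome. The first is HF while the current is applied; the second is HF outside stimulation.

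Two things are at stake. The first is the data: a pre or post EKG that was not recorded at the visit cannot be obtained later. The second is interpretation. HF during stimulation reflects a response to ongoing current, whereas HF afterwards reflects an after-effect. A result on one does not answer the question about the other, and 2.4.1 does not choose between them. The Study Summary names EKG biomarker data for the design of later studies as part of the trial's purpose, so the trial should be able to say which quantity it estimated.

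**Working it through.** The documents give no numerical figure to reproduce, because section 11.2 declines a sample size calculation. The check sets the sections side by side, with simple arithmetic on the durations.

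**1. What is recorded and what is needed, per visit**

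| | 6.3.2 and 7.2 | 11.1 |
|---|---|---|
| Window | during stimulation | before and after stimulation |
| EKG described in that window | 40 min | 0 min |
| Segment | one of 40/10 = 4 intervals, none designated | length not stated |
| Spectral components | total, HF, LF, VLF | total, HF, LF, HP |

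**2. Could a 6.3.2 interval serve as pre or post?** Section 4 gives the active condition 10 + 2400 + 10 = 2420 s of current and sham 10 + 60 + 10 = 80 s. The recording lasts 40 min = 2400 s. On the active visit all four intervals therefore lie within stimulation, so none is a pre or a post interval. On the sham visit the current stops 80 s after it starts. Comparing matching intervals thus compares current with little or no current, which is not the after-effect that 11.1 implies.

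**3. Could the data come from elsewhere?** The only physiological recordings described on either side of stimulation are the resting EEG blocks, 5 + 5 = 10 min per visit. The ECG leads are part of the EEG system, so the channel could run then, but no section says that it does. A 10-minute segment would not fit in a 5-minute block. That is not a second contradiction, because 11.1 does not ask for 10 minutes. The missing Appendix A row is weak evidence, because the resting EEG has no row there either.

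**4. Place of the pre value (secondary point).** The 11.1 model has session and treatment only. It states no change score, pre/post factor or baseline covariate.

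An illustration of how much this could matter, on assumed correlations because the documents give none: take log HF with variance 1, within-visit pre-post correlation rw, a common between-visit correlation rb, and rw > rb. Let rho = (rw − rb)/(1 − rb). The variance of a participant's active-sham difference is

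- post alone: 2(1 − rb)
- post minus pre: 4(1 − rw)
- post adjusted for pre: 2(1 − rb)(1 − rho²)

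Relative to the adjusted analysis, post alone is 1/(1 − rho²) and post minus pre is 2/(1 + rho):

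| rw, rb | rho | post alone | post minus pre |
|---|---|---|---|
| 0.6, 0.5 | 0.20 | 1.04 | 1.67 |
| 0.7, 0.5 | 0.40 | 1.19 | 1.43 |
| 0.8, 0.4 | 0.67 | 1.80 | 1.20 |

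As rw falls to rb, rho goes to 0 and the ratios go to 1.00 and 2.00. These figures compare ways of using the pre value. They do not measure the difference between HF during and HF after stimulation, and the conclusion does not rest on them.

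**The case against.** The strongest reply is that no data need be lost: the ECG leads are on the EEG system, EEG is recorded before and after stimulation, and a technician would probably leave the channel running. This stands as far as it goes. A reader might infer that the primary data will certainly be missing, and the documents do not support that. They support a risk, which arises because the plan leaves the recording to local habit.

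Other readings also go too far:

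- **Many rival primary outcomes.** A reader might count each 10-minute interval, their mean, the post value and the change score as competing primaries. Only 11.1 carries the primary label. Section 6.3.2 is a procedures section, and its wording can mean that every interval is analysed. The firm conflict is two-way: during stimulation against pre and post.
- **An invalid ANOVA.** A reader might infer that the missing role for the pre value invalidates the test. It does not. With randomised order, the active-sham contrast is valid without a baseline term, and a change score would fit the stated factors. The gap is one of specification and precision.
- **Mis-sized later trials.** Section 11.2 says the results will set future sample sizes but does not name HF, and the Study Summary lists pilot efficacy beside the EKG data. A specific error in a later sample size cannot be derived from the documents.

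**Conclusion.** The point holds and should be settled before data collection, because it concerns the primary outcome. Followed literally, 6.3.2 yields 40 minutes of EKG per visit and none in the windows that 11.1 analyses. No 6.3.2 interval can stand in for those windows on the active visit.

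This conclusion rests on the text alone and needs no assumed value. Whether data are actually lost depends on whether the ECG channel runs during the resting EEG, which the documents leave open. The unstated role of the pre value is a lesser matter of precision, and its size is unknown without HF correlations from this population.

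**What to change.** 1. State in 5.2.1, 5.2.2, 6.3.2 and Appendix A that the ECG channel also runs through the existing 5-minute pre and 5-minute post resting EEG blocks. Sections 5.2.1 and 5.2.2 do not say where these blocks fall relative to the sit-to-stand, fingertip-to-floor and pressure-pain tests. Fix that order and keep it the same at both visits, so that any effect of the tests on heart rate is shared by active and sham.
2. Make HF in the post-stimulation block the primary measure, since 11.1 carries the primary label. Give the same window and length in 2.4.1, 6.3.2 and 11.1, and the same list of spectral components in 6.3.2 and 11.1. Report HF during stimulation as supportive, saying how the four intervals are used.
3. Use the same visit's pre-block HF as a covariate in a model with participant, session and treatment. With 20 completers this leaves 40 − 20 − 1 − 1 − 1 = 17 residual degrees of freedom, against 18 without the covariate. At the second visit the pre value relies on the washout and equal-carryover assumption already made in 11.1.
4. Remove or reconcile the description of heart rate as a covariate in 7.2. A value recorded during stimulation may itself respond to treatment, so it cannot play the part of a baseline.

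**Cost.** Protocol wording, plus 10 min of ECG per visit: 10 × 2 = 20 min per participant and 20 × 20 = 400 min in all, within blocks already scheduled. No extra visit or device is needed. The downsides are shorter segments (frequency resolution 1/300 = 0.0033 Hz instead of 1/600 = 0.0017 Hz) and leads that must be in place for both blocks, or refitted if tests come between. If sessions have already been run, first check whether their EEG files contain the ECG channel.
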